Study Protocol

Randomized Evaluation of Heart Failure with Preserved Ejection Fraction (HFpEF) Patients with Acute Heart Failure and Dopamine (ROPA-OP) Trial

clinicaltrials.gov Identifier: NCT01901809

Protocol Date: August 8, 2013

Principal Investigator:

[name]

The Johns Hopkins University School of Medicine.

[name]

[name]

[contact] [contact]

JHM IRB - eForm A – Study Protocol

- Use the section headings to write the JHM IRB eForm A, inserting the appropriate material in each. If a section is not applicable, leave heading in and insert N/A.
- When submitting JHM IRB eForm A (new or revised), enter the date submitted to the field at the top of JHM IRB eForm A.

1. Abstract

- a. Provide no more than a one page research abstract briefly stating the problem, the research hypothesis, and the importance of the research.

Heart Failure with preserved Ejection Fraction (HFPEF) accounts for 40-50% of all heart failure patients with a frequency of hospital admissions for acute decompensation and short and long term mortality similar to patients with heart failure with reduced ejection fraction (HFREF). Patients with HFPEF are often preload dependent and despite admission to the hospital for acute decompensated heart failure (ADHF), are typically difficult to diurese due to the development of acute kidney injury. In contrast to the many randomized trials showing mortality and morbidity benefit of ACE inhibitors and beta blockers in patients with heart failure with reduced ejection fraction, no drugs have shown a benefit in patients with HFPEF. Furthermore, patients hospitalized for ADHF who develop acute kidney injury during their hospital stay have longer hospitalizations, more frequent re-hospitalizations for heart failure, and worse short term survival compared to those without acute kidney injury. We hypothesize that changing the method of diuresis and/or the addition of low-dose dopamine for the treatment of ADHF in patients with HFPEF will reduce renal injury, resulting in a shorter length of stay, and decrease hospital readmissions over the ensuing year.

2. Objectives (include all primary and secondary objectives)

To evaluate the effects of low dose dopamine and diuretic strategy (intermittent versus continuous) on renal function in patients with HFPEF admitted with acute heart failure.

Primary end point:

1. Percent change in creatinine from randomization to 72 hrs from treatment protocol initiation.

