8. Patient Global Well being assessment by VAS*
9. Dyspnea assessment by VAS*
10. Frailty Index*
11. Changes in cardiovascular medications
12. Assessment for serious cardiovascular events
13. Urine and serum samples for biomarkers*

*Investigational data to be collected as part of trial protocol.

Day 30, 6 month, and 1 year Assessment and Data to be Recorded:

Patient charts will be reviewed and patients will receive a phone call to assess for potential re-hospitalizations and major adverse cardiovascular events at each respective endpoint since discharge. The first readmission event following index hospitalization will be adjudicated by a Clinical Event Committee consisting of 2-3 cardiologists not directly in contact with patients enrolled in the study.

Vascular Access:

All patients in the intermittent bolus diuretic strategy arm will require the placement of two functioning peripheral IV catheter. Patients assigned to the continuous diuretic strategy and either treatment arm that requires low-dose dopamine will need at least 2 peripheral IVs suitable for continuous infusions. Central venous catheter placement may be required should it be difficult to obtain or maintain peripheral IV

access. This would be determined by the primary team, with consent obtained separately for this procedure by the primary team.

Foley Catheter Placement:

All patients enrolled in this trial will be encouraged to have a foley urinary catheter placed. This will allow for improved patient tolerance of diuresis and improved accuracy of I/O assessment by nursing staff. This will not be required, however, for enrollment in the trial.

b. Study duration and number of study visits required of research participants.

The study duration is the hospital admission. The study drugs will be mandated for 72 hours following enrollment. There are no outpatient visits but patients will receive follow up phone calls, at 30 days and at 6 months following discharge.

c. Blinding, including justification for blinding or not blinding the trial, if applicable.

The treatment is not blinded. The primary endpoint of change in renal function will be objectively obtained and should not be affected by lack of blinding. All other variables will be obtained by an investigator blinded to the study drug assignment.

d. Justification of why participants will not receive routine care or will have current therapy stopped.

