6. Drugs/ Substances/ Devices

a. The rationale for choosing the drug and dose or for choosing the device to be used.

Furosemide is that standard of care diuretic for patients admitted to the hospital for acute decompensated heart failure. Dopamine at low dose is often used to assist diuresis and reduce acute kidney injury in patients at high risk for acute kidney injury with heart failure from systolic dysfunction.

b. Justification and safety information if FDA approved drugs will be administered for non-FDA approved indications or if doses or routes of administration or participant populations are changed.

N/A.

c. Justification and safety information if non-FDA approved drugs without an IND will be administered.

N/A

7. Study Statistics

a. Primary outcome variables.

1. Percent change in creatinine from randomization to 72 hrs from treatment protocol initiation.

b. Secondary outcome variables.

1. Change in incidence of acute kidney injury (AKI) as defined by Kidney Disease: Improving Global Outcomes (KDIGO criteria summarized below) from randomization to 72 hrs.¹
2. Incidence of AKI as determined by urine output at 72 hrs (KDIGO criteria, summarized below).¹
3. Change in creatinine at 72 hrs adjusted for volume of fluid removal
4. Change in serum cystatin C randomization to 72 hrs
5. Change in NT pro-BNP from randomization to 72 hrs
6. Volume of diuresis measured in liters
 - c) Cumulative volume of diuresis measured in liters
 - d) Cumulative volume of diuresis measured in liters adjusted for BSA
7. Net weight loss at 72 hrs in kg
8. Need for increase in intravenous diuretic dose
9. Change in distance during 6 minute walk test
 - c) From admission to 72 hrs
 - d) From admission to discharge
10. Global well-being assessment score from admission to 72 hrs, and at discharge. To be assessed by a Visual Analog Scale (VAS).
11. Subjective dyspnea score from admission to 72 hrs, and at discharge. To be assessed by a Visual Analog Scale (VAS).
12. Change in frailty index from admission to 72 hrs, and at discharge. To be assessed by the Johns Hopkins Older Americans Independence Center Online Frailty Assessment Tool
13. Length of stay of hospitalization in days

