14. 30 day, 6 month, and 1 year hospital readmission or ER visit for major adverse cardiovascular event, heart failure, renal failure (development of CKD, ESRD, or dialysis need by KDIGO criteria), syncope, or arrhythmia. Readmission events will be adjudicated by a Clinical Event Committee consisting of 2-3 cardiologists not directly in contact with patients enrolled in the study.

KDIGO AKI Definition¹:

AKI is defined by any of the following 3 criteria:

1. Increase in serum creatinine by ≥ 0.3 mg/dl (≥ 26.5 $\mu\text{mol/l}$) within 48 hours; OR
2. Increase in serum creatinine to ≥ 1.5 times baseline, which is known or presumed to have occurred within prior 7 days; OR
3. Urine volume < 0.5 ml/kg/h for 6 hours

Stages of AKI as defined by KDIGO Criteria are as follows:

Stage	Serum Creatinine	Urine Output
1	1.5-1.9 times baseline OR ≥ 0.3 mg/dl (≥ 26.5 $\mu\text{mol/l}$) increase	< 0.5 ml/kg/h for 6-12 hours
2	2.0-2.9 times baseline	< 0.5 ml/kg/h for ≥ 12 hours
3	3.0 times baseline OR increase in serum creatinine to ≥ 4.0 mg/dl (≥ 353.6 $\mu\text{mol/l}$) OR initiation of renal replacement therapy OR, in patients < 18 years, decrease in eGFR to < 35 ml/min per 1.73 m ²	< 0.3 ml/kg/h for ≥ 24 hours OR Anuria for ≥ 12 hours

a. Statistical plan including sample size justification and interim data analysis.

1. Overview:

- a. This is a factorial design study evaluating two simultaneous unrelated interventions. Sample size justification and primary endpoint analysis is described below.

2. Analysis of Primary Endpoints:

- a. The primary analysis will be conducted on an intention-to-treat basis. Non-parametric testing for the continuous primary endpoint (creatinine) will be performed using the Wilcoxon-Mann-Whitney U test. Confirmatory test for interaction between dopamine and diuretic strategy will be performed with linear regression analysis with dopamine*diuretic term, $p=0.10$ for significance.

3. Sample Size Justification:

- a. A difference of 30% in creatinine pre and post- treatment is considered to be clinically meaningful. Setting parameters as follows: two-sided, alpha (Type I error rate) of 0.05, power of 0.80, and using mean creatinine calculations based on our own retrospective experience at

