Johns Hopkins as well as data from prior studies in patients admitted with ADHF, we estimate a sample size of approximately 63 patients per treatment arm. This translates to 63 patients assigned to the diuretic-only treatment arm (intermittent bolus and continuous) and 63 patients assigned to the low-dose dopamine arm (in addition intermittent bolus diuretic and continuous diuretic treatment). Taking into account drop-out rate, we plan to enroll 140 patients (70 per treatment arm; 34 per specific treatment strategy).

4. Randomization:

- a. Patients will be randomized in a blinded fashion to one of four treatment arms upon enrollment. We plan to perform block randomization into the treatment arms and plan to stratify patients by race, CKD status, and receipt of IV contrast dye (during the same admission), as these factors are felt to be significantly associated with the development of AKI.

5. Analysis of Secondary Endpoints:

- a. Summaries of continuous variables will be displayed using the mean, standard deviation, and median. For nominal variables, the number and frequency of subjects in each category will be presented. Statistical tests with p-values < 0.05 will be considered statistically significant, unless otherwise stated.

b. Early stopping rules.

A study subject will be removed from the trial if the above mentioned scenarios from Section 5 were to occur:

- i. The development of hemodynamic instability including hypotension (SBP < 90), hypertensive emergency, or unstable arrhythmias (SVT or VT)
- ii. The development of pulmonary edema requiring inotropes or vasopressor or more than 50% inspired oxygen.
- iii. The development of acute coronary syndrome.
- iv. The development of acute kidney injury as follows:
 - a. If the patient develops Stage II AKI (by KDIGO criteria)¹, the study treatment will be held and a clinical decision will be made whether to resume or discontinue treatment drug
 - b. If the patient develops Stage III AKI (by KDIGO criteria)¹, the study treatment will be discontinued and the patient will be classified as treatment failure and followed only for outcome recording.
 - i. The need for renal replacement therapy
 - ii. New atrial fibrillation or other supraventricular tachyarrhythmia
 - iii. Sustained ventricular arrhythmias

- v. Requirement of furosemide dose increase beyond the study maximum of 200 IV twice daily (or 400 IV over 24 hrs), or the need for addition of thiazide diuretic.

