All patients will be admitted to telemetry floor beds for close monitoring of hemodynamic state. All patients will undergo vital sign checks every 4-8 hrs depending on clinical stability. Standard of care for inpatient acute heart failure management includes twice daily basic metabolic profile check to assess renal function and electrolytes. A standardized electrolyte replacement protocol will be enforced for all patients to minimize the risk of cardiac arrhythmias in the setting of diuresis. In patients whose GFR is below and/or creatinine is above the cutoff for the standard electrolyte repletion protocol, this will be managed by the primary team physicians. In addition, the

above stated exclusion criteria are designed to minimize enrollment of patients who are apt to have side effects.

A subject will not be considered for enrollment if they have any signs of hemodynamic instability (please refer to Exclusion criteria). This includes hypotension for any reason (SBP < 90), hypertensive emergency (SBP >200 or signs of end-organ damage), supraventricular tachycardias (atrial fibrillation, atrial flutter) that are not responsive to rate control therapies, or ventricular arrhythmias beyond occasional PVCs or NSVT.

In the dopamine strategy group, if the subject develops tachycardia as defined by heart rate of >120 beats per min the infusion will be stopped. After 3 hours, if heart rate is < 120 beats per min, the IV infusion will be restarted at 1 µg/kg/min (<50% of the previous dose). If the heart rate is >120 beats per min after 3 hours or if tachycardia recurs, then the infusion will be terminated and this will be captured as “treatment failure.”

c. Plan for reporting unanticipated problems or study deviations.

All unanticipated problems such as transfers to the CCU, atrial or ventricular arrhythmias, acute coronary syndrome, or acute renal failure requiring renal replacement therapy will be reported within 48 hrs and reviewed by the study team. All deaths will be reviewed by the study team and reported to the IRB.

d. Legal risks such as the risks that would be associated with breach of confidentiality.

e. Financial risks to the participants.

There is no financial risk to the patients in this study.

9. Benefits

a. Description of the probable benefits for the participant and for society.

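### No endpoint counts death, so under the stated frequency analysis higher mortality in an arm lowers, other things equal, its readmission rate (secondary endpoint 14)

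*Combined protocol and SAP*

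**What the plan says.** Item 14 of the secondary endpoints (Section 2, repeated in Section 7.b) is "30 day, 6 month, and 1 year hospital readmission or ER visit for major adverse cardiovascular event", with heart failure, renal failure, syncope and arrhythmia as the other qualifying reasons. Item 13 is "Length of stay of hospitalization in days". No primary or secondary endpoint counts death.

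Other provisions that bear on this:

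- **Collection (Section 4.a, day 30, 6 month and 1 year assessment).** Charts are reviewed and "patients will receive a phone call to assess for potential re-hospitalizations and major adverse cardiovascular events at each respective endpoint since discharge". Major adverse cardiovascular events (MACE) are not defined anywhere.
- **Adjudication (same place).** "The first readmission event following index hospitalization will be adjudicated by a Clinical Event Committee". Adjudication of deaths is not mentioned.
- **Analysis (Section 7, statistical plan, item 5).** "For nominal variables, the number and frequency of subjects in each category will be presented", and "Statistical tests with p-values < 0.05 will be considered statistically significant, unless otherwise stated". There is no time-to-event method, no competing-risk method, no censoring rule and no rule for deaths.
- **Deaths (Section 8.c).** "All deaths will be reviewed by the study team and reported to the IRB". This is safety reporting and not a comparison of arms.
- **Expected mortality (Section 1).** The abstract describes "short and long term mortality similar to patients with heart failure with reduced ejection fraction" and gives no rate. Section 3 puts morbidity and mortality level with, or a little better than, that comparison group.

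**The concern.** In item 14 the cardiovascular event is a reason for a readmission or ER visit. Even if MACE was meant to include cardiovascular death, a death at home or during the index stay involves no readmission and does not meet the definition. With all randomized patients in the denominator, someone who dies on day 20 without a qualifying visit is recorded as having no event at 30 days, 6 months and 1 year.

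Death removes patients from the risk of readmission. If mortality differs between arms, the readmission percentages differ even when the treatments have the same effect on readmission, and the difference favours the arm with more deaths. Item 14 is secondary, but the abstract's hypothesis names fewer readmissions over the following year alongside less renal injury and a shorter stay. Length of stay has a related gap, because nothing says how a stay that ends in death is scored.

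**Working it through.** **Plan's own figure.** There is none to reproduce for item 14: no readmission rate, death rate or power is given. The only design figure is for creatinine, 63 per side raised to 70 for drop-out (63/0.90 = 70, which fits an unstated 10%). I use 70 per side of the dopamine comparison.

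**Assumptions, not from the documents.** Constant, independent hazards; a readmission hazard λ = 0.5 per year in both arms; 1-year mortality m of 10%, 20% or 30%; all patients start follow-up together and stay in the denominator.

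**Formulas**, with t in years:

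- Death hazard: h = −ln(1 − m), giving 0.1054, 0.2231 and 0.3567.
- Counted as readmitted by t: R(t) = λ/(λ + h) × [1 − exp(−(λ + h)t)].
- Death or readmission by t: C(t) = 1 − exp(−(λ + h)t).

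**At 1 year:**

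- m = 10%: C = 1 − exp(−0.6054) = 45.4%; R = (0.5/0.6054) × 45.4% = 37.5%.
- m = 20%: C = 1 − exp(−0.7231) = 51.5%; R = (0.5/0.7231) × 51.5% = 35.6%.
- m = 30%: C = 1 − exp(−0.8567) = 57.5%; R = (0.5/0.8567) × 57.5% = 33.6%.

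**By time point, mortality 10% vs 20%:**

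| Time | Readmitted, 10% arm | Readmitted, 20% arm | False advantage (points) |
|---|---|---|---|
| 30 days (t = 30/365) | 4.01% | 3.99% | 0.02 |
| 6 months (t = 0.5) | 21.6% | 21.0% | 0.6 |
| 1 year (t = 1) | 37.5% | 35.6% | 1.9 |

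At 1 year the composite is 51.5 − 45.4 = 6.1 points worse in the arm with more deaths. For mortality of 10% vs 30%, the 1-year false advantage is 37.5 − 33.6 = 3.9 points and the composite is 57.5 − 45.4 = 12.1 points worse.

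**Size against sampling error.** With 70 per side, the standard error of the 1-year difference is √[(0.375 × 0.625 + 0.356 × 0.644)/70] = 8.1 points. The 1.9-point shift is about 1.3 patients, or 0.24 standard errors. It raises the chance of a significant result favouring the arm with more deaths from 2.5% to about 4%; for 10% vs 30% it is about 7%.

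**Sensitivity.** I varied the 1-year readmission risk without deaths over 30% to 60%, and the mortality contrasts over 10% vs 20%, 10% vs 30%, 20% vs 30% and 20% vs 40%. The false advantage at 1 year runs from 1.5 to 5.9 points and the composite disadvantage from 4 to 14 points. In every case the two measures point in opposite directions.

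**The case against.** **The plan is silent on deaths; it does not call them successes.** A reader might infer that it does, but no sentence says so. The no-event status follows from the definition, the number-and-frequency summary and a full intention-to-treat denominator. Dropping patients who die unreadmitted would change the result: in the example, 37.5/(100 − 7.9) = 40.7% vs 35.6/(100 − 15.9) = 42.3%, where 7.9 and 15.9 are C − R. That would exclude patients on an outcome after randomization, so it is no remedy. It does show that the rule must be written down.

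**MACE is collected at follow-up separately from re-hospitalization, and deaths are reviewed.** Both are true, and a large imbalance in deaths would probably be noticed. But the term is undefined, and neither provision puts death into a comparison of arms.

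**The effect is small and depends on a mortality difference.** This stands. Treatment lasts at most 72 hours, and nothing in the documents suggests that it doubles 1-year mortality. A higher readmission hazard in the arm with more deaths could outweigh the shift, and at 30 days the shift is negligible.

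**Two stronger readings are not supported.** A reader might infer that the protocol calls mortality in this population high. Sections 1 and 3 make only a comparison with reduced-ejection-fraction heart failure and give no rate. A reader might also infer that the trial could declare benefit where there is harm. At 0.24 standard errors, that is remote through this mechanism alone.

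**Length of stay.** An in-hospital death can follow a long stay, and the documents give neither the rate nor the timing of such deaths. Only the missing rule is established; no direction or size of bias can be given.

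**Conclusion.** The point holds in a limited form. Death is in no listed endpoint, and under the stated analysis a patient who dies without a qualifying visit has no event in item 14. Other things equal, this favours an arm with higher mortality. Under the assumed rates (readmission hazard 0.5 per year in both arms, 1-year mortality 10% vs 20%), the 1-year shift of 1.9 points favours that arm, while death-or-readmission puts it 6.1 points behind. These figures illustrate direction and scale and do not predict this trial's results. Item 14 is secondary and the shift is well within sampling error, so the primary creatinine analysis is untouched. The change is still worth making, because the distortion runs the wrong way on an outcome in the stated hypothesis and is cheap to prevent.

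**What to change.** Keep item 14 as it stands and add the following:

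1. A companion endpoint: death from any cause or first qualifying readmission or ER visit, at 30 days, 6 months and 1 year, with each component shown by arm.
2. All-cause deaths by arm at the same time points.
3. For readmission alone, cumulative incidence with death as a competing event.
4. A definition of MACE that says whether it includes death.
5. Vital status recorded at the existing chart reviews and calls. Section 4.a has follow-up at 30 days, 6 months and 1 year, but Section 4.b lists calls only at 30 days and 6 months. The two must be reconciled so that 1-year status is covered.
6. For length of stay, rank in-hospital deaths as the worst outcome or report them separately.

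The cost is mainly wording, plus a vital-status field and, if it is not already intended, a 1-year call. The section on reporting deaths does not by itself guarantee vital status at 1 year. The downside of the composite is that it mixes death with readmission, so the components must always be shown. The composite is not powered either: in the example its 6.1-point difference has a standard error of √[(0.454 × 0.546 + 0.515 × 0.485)/70] = 8.4 points. Its purpose is to remove a bias, not to provide a decisive test.

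### Secondary endpoint 14 counts only readmissions and ER visits and the plan has no rule for death, so the 1-year comparison can modestly favour an arm with more deaths

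*Combined protocol and SAP*

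**What the plan says.** Item 14 has the same wording in section 2 (Objectives) and section 7.b (Secondary outcome variables): "30 day, 6 month, and 1 year hospital readmission or ER visit for major adverse cardiovascular event, heart failure, renal failure", followed by syncope and arrhythmia. The primary endpoint and the other 13 secondary endpoints do not include death.

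The committee's remit is also limited to readmission: "Readmission events will be adjudicated by a Clinical Event Committee consisting of 2-3 cardiologists". Section 4.a narrows it to one event per patient: "The first readmission event following index hospitalization will be adjudicated by a Clinical Event Committee".

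For follow-up, section 4.a provides for a review of charts and adds: "patients will receive a phone call to assess for potential re-hospitalizations and major adverse cardiovascular events at each respective endpoint since discharge". The contacts there are at 30 days, 6 months and 1 year. Section 4.b lists calls at 30 days and 6 months only. Major adverse cardiovascular event is not defined anywhere.

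Deaths appear as a reporting matter in section 8.c: "All deaths will be reviewed by the study team and reported to the IRB".

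The analysis text for secondary endpoints (section 7, Statistical plan, item 5) says: "For nominal variables, the number and frequency of subjects in each category will be presented". It adds: "Statistical tests with p-values < 0.05 will be considered statistically significant, unless otherwise stated". It names no time-to-event method, no censoring rule and no rule for patients who die first.

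**The concern.** Death removes a patient from the risk of readmission. A patient who dies at home on day 20, or during the index stay, can never have a qualifying visit. In a table of readmitted v not readmitted, that patient sits with those who did well, while a patient readmitted on day 40 who survives sits with the failures.

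The undefined term for major adverse cardiovascular events does not close the gap. In item 14 it is only a reason for a readmission or ER visit, so a death without a hospital contact still does not qualify. A death learned of at a follow-up call has no stated route into the endpoint.

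The point matters because fewer readmissions over the following year is part of the hypothesis in the Abstract. The Abstract also describes short- and long-term mortality as similar to that in heart failure with reduced ejection fraction, so deaths should be expected over a year. Section 8.a lists ventricular arrhythmia among the serious but uncommon risks of dopamine, so equal survival cannot simply be assumed. A readmission result read alone could look neutral or favourable while survival was worse.

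**Working it through.** The plan gives no rate, event count or power for item 14, so there is no figure to reproduce. The calculation below shows direction and size only.

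**Inputs.** From the documents: 70 patients per pooled arm (sample size section) and the three time points. Assumed: constant hazards, the same readmission hazard in both arms, a 1-year qualifying-readmission risk r of 30% or 50% if nobody died, and a 1-year mortality d of 15% in one arm and 30% in the other. Deaths without a qualifying visit are counted as not readmitted. All patients start at a common origin, and index-stay deaths are not modelled separately.

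**Formulas.** Hazards: h_r = −ln(1 − r) and h_d = −ln(1 − d). With t in years and 30 days taken as 30/365:
- Observed readmission = h_r/(h_r + h_d) × [1 − exp(−(h_r + h_d)t)]
- Death without readmission = h_d/(h_r + h_d) × the same bracket
- Death or readmission = the bracket itself

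**One year, r = 30%.** h_r = 0.357; h_d = 0.163 (15%) or 0.357 (30%).
- Lower-mortality arm: bracket = 1 − 0.70 × 0.85 = 0.405; readmission = 0.687 × 0.405 = 27.8%.
- Higher-mortality arm: bracket = 1 − 0.70 × 0.70 = 0.510; readmission = 0.500 × 0.510 = 25.5%.

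**One year, r = 50%.** h_r = 0.693.
- Lower-mortality arm: 0.810 × 0.575 = 46.6%.
- Higher-mortality arm: 0.660 × 0.650 = 42.9%.

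**All time points, lower- v higher-mortality arm:**

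| Time | Readmission, r = 30% | Readmission, r = 50% | Apparent advantage of the higher-mortality arm |
|---|---|---|---|
| 30 days | 2.87% v 2.85% | 5.50% v 5.46% | 0.02 to 0.04 points |
| 6 months | 15.7% v 15.0% | 28.2% v 27.0% | 0.7 to 1.2 points |
| 1 year | 27.8% v 25.5% | 46.6% v 42.9% | 2.3 to 3.7 points |

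At 1 year the advantage is 1.6 to 2.6 patients of 70. Counting death as an event reverses the sign: 40.5% v 51.0% (r = 30%) and 57.5% v 65.0% (r = 50%), which is 10.5 and 7.5 points against the higher-mortality arm. Deaths without a qualifying visit number about 8.9 v 17.9 of 70 (r = 30%) or 7.6 v 15.5 of 70 (r = 50%).

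**Sensitivity.** With mortality of 15% v 20%, the 1-year distortion falls to 0.8 to 1.2 points, under one patient of 70. Over readmission risks of 30 to 60%, with mortality of 10% v 20%, 10% v 30% and 5% v 15%, it runs from 1.5 to 5.6 points at 1 year and is 0.1 point or less at 30 days.

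**The case against.** A reader might infer that the plan scores a dead patient as readmission-free. It does not say so. It is silent, and censoring, exclusion or a separate category are not ruled out. What stands is that a count by category is the only stated summary, so not readmitted is the default. If censoring or exclusion was intended, that too needs to be written down.

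A reader might also infer that the arm with more deaths will look better at all three time points. The documents do not support that either. The direction depends on similar readmission hazards, and an arm with worse heart failure or kidney injury could have more deaths and more readmissions. At 30 days the effect after discharge is close to nil. At 1 year, 2.3 to 3.7 points compares with a standard error of 7.5 to 8.4 points at 70 per arm.

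The assumed contrast is large: mortality doubles after study treatment of at most 72 hours. The documents give no mortality rate. The Background calls morbidity and mortality equal to or slightly better than with reduced ejection fraction, and the exclusions remove sepsis and non-cardiac terminal illness with expected survival under a year. A smaller contrast gives a smaller distortion, as the sensitivity check shows.

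A composite would not reliably detect the harm. In the scenarios above its power at 1 year is about 15 to 24%. That is a fair limit on what the fix achieves, but it does not justify a definition that leaves deaths out of the comparison.

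Finally, it is tempting to say that the remedy needs no new data because deaths are already reviewed. That does not hold: section 8.c sets up no vital-status follow-up, section 4.a does not name all-cause death, and section 4.b omits the 1-year call.

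**Conclusion.** The concern holds as a gap in the endpoint definition and its analysis. Item 14 leaves out death, no other endpoint captures it, and nothing says how a patient who dies first is counted. Under the default count, and if readmission hazards are similar, the comparison leans towards the arm with more deaths: negligibly at 30 days, by about 1 point at 6 months, and by about 2 to 4 points at 1 year. Those sizes rest on assumed mortality of 15% v 30%, an assumed readmission risk of 30 to 50% and constant hazards; none comes from the documents.

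The distortion is a few patients per arm, on a secondary endpoint. It should still be corrected, because the endpoint serves a stated hypothesis and the correction is cheap. The primary 72-hour creatinine analysis and its sample size are unaffected.

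**What to change.** Amend item 14 in sections 2 and 7.b, and the secondary analysis text, in one of two ways:

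1. Make the event death from any cause or first adjudicated qualifying readmission or ER visit, read out at 30 days, 6 months and 1 year, with the components shown separately.
2. Keep readmission or ER visit as the event and report its cumulative incidence with death as a competing event, beside the cumulative incidence of death. With complete follow-up, the readmission curve alone gives the same figure as the raw proportion, so the death curve must be read with it.

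In either case:
- count deaths during the index stay;
- state the time origin (section 4.a now counts from discharge, which leaves index-stay deaths out; randomisation would include them);
- define major adverse cardiovascular event;
- report all-cause death by arm;
- record vital status and date of death at each chart review and call;
- reconcile section 4.b with section 4.a on the 1-year contact.

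The cost is small: endpoint and analysis wording, one added data item at contacts that section 4.a already plans, and, for the composite, some noise from deaths unrelated to treatment, which the separate components make visible.
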